**CHECKLIST FOR PATIENT ELIGIBILITY FOR TREATMENT**

YES	NO	VALUE/DATE	
Any "NO" answers will make a patient ineligible for study participation.			
			18 years or older
			Confirmed SARS-CoV2 infection real-time reverse transcription polymerase chain reaction (RT-PCR) assay
			Moderate OR severe acute respiratory distress syndrome (ARDS), based on the degree of impairment of oxygenation as defined by the ratio of arterial oxygen tension to fraction of inspired oxygen (PaO 2 /FiO 2 ): a. Moderate ARDS: PaO 2 /FiO 2 100-200 mmHg OR b. Severe ARDS: PaO 2 /FiO 2 ≤100 mmHg
			If on invasive or non-invasive (BiPAP) mechanical ventilator, PEEP ≥5 cm H 2 O
			Bilateral opacities present on chest radiograph or computed tomographic (CT) scan, that are not fully explained by pleural effusions, lung collapse, or lung nodules.
YES	NO	VALUE/DATE	
Any "YES" answers will make a patient ineligible for study participation.			
			Currently receiving extracorporeal membrane oxygenation (ECMO)
			Severe chronic respiratory disease requiring current use of home oxygen prior to COVID-19 diagnosis
			Pregnant or lactating
			Known hypersensitivity to dimethyl sulfoxide (DMSO)
			Unstable hemodynamics as deemed by the treating physician/investigator including but not limited to unstable , ventricular tachycardia or new cardiac arrhythmia requiring cardioversion
			Uncontrolled bacterial or fungal co-infection
			Any end-stage organ disease or condition, which in the opinion of the Investigator, makes the patient an unsuitable candidate for treatment
			Inability to obtain informed consent (from patient or legally appropriate proxy)
			Presence of any contraindication to receiving prophylactic low dose unfractionated or low molecular weight heparin
			Respiratory failure explained or complicated by cardiac failure or fluid overload

Signature of MD \_\_\_\_\_ Date \_\_\_\_\_

## PROTOCOL SYNOPSIS

### Single Donor Banked Bone Marrow Mesenchymal Stromal Cells for the Treatment of COVID-19 Induced ARDS: A Non-Blinded Randomized Controlled Study

**Principal Investigator:** [name]

**Study Design:** Single center, open-label, non-blinded randomized controlled study

**Objective:** To evaluate the safety and clinical benefits of banked mesenchymal stromal cells (MSCs) versus controls for treatment of patients with ARDS due to COVID-19

**Eligibility Criteria:**

**Inclusion Criteria**

- 1) 18 years or older
- 2) Confirmed SARS-CoV2 infection real-time reverse transcription polymerase chain reaction (RT-PCR) assay
- 3) Moderate **OR** severe acute respiratory distress syndrome (ARDS), based on the degree of impairment of oxygenation as defined by the ratio of arterial oxygen tension to fraction of inspired oxygen ( $\text{PaO}_2/\text{FiO}_2$ ):
  - a. Moderate ARDS:  $\text{PaO}_2/\text{FiO}_2$  100-200 mmHg
  - OR**
  - b. Severe ARDS:  $\text{PaO}_2/\text{FiO}_2 \leq 100$  mmHg
- 4) If on invasive or non-invasive (BiPAP) mechanical ventilator PEEP  $\geq 5$  cm H2O
- 5) Bilateral opacities present on chest radiograph or computed tomographic (CT) scan, that are not fully explained by pleural effusions, lung collapse, or lung nodules.

**Exclusion Criteria**

- 1) Currently receiving extracorporeal membrane oxygenation (ECMO)
- 2) Severe chronic respiratory disease requiring current use of home oxygen prior to COVID-19 diagnosis
- 3) Pregnant or lactating
- 4) Known hypersensitivity to dimethyl sulfoxide (DMSO)
- 5) Unstable hemodynamics as deemed by the treating physician/investigator including but not limited to unstable, ventricular tachycardia or new cardiac arrhythmia requiring cardioversion

- 6) Uncontrolled bacterial or fungal co-infection
- 7) Any end-stage organ disease or condition, which in the opinion of the Investigator, makes the patient an unsuitable candidate for treatment
- 8) Inability to obtain informed consent (from patient or legally appropriate proxy)
- 9) Presence of any contraindication to receiving prophylactic low dose unfractionated or low molecular weight heparin
- 10) Respiratory failure not fully explained by cardiac failure or fluid overload.

## 1 Background and Rationale

### 1.1 Acute Respiratory Distress Syndrome (ARDS)

Acute respiratory distress syndrome (ARDS) is an acute, life-threatening form of respiratory failure caused by diffuse inflammatory mediated alveolar injury leading to impaired gas-exchange, decreased compliance and fluid accumulation in the airspaces. Excessive inflammation is a major contributor to lung injury in ARDS leading to activation of the complement system by alveolar macrophages and the release of pro-inflammatory cytokines such as TNF, IL-1, IL-6, and IL-17, as well as multiple chemokines such as IL-8, CCL-2, and CCL-7 [1]. This leads to the accumulation of neutrophils and monocytes to the site of injury where they release toxic substances that damage the capillary endothelium and alveolar epithelium [1]. The ensuing cytokine storm leads to systemic inflammatory response, septic shock, and multi-organ failure [2, 3]. Multiple etiologies may trigger ARDS, including respiratory infections, sepsis/shock, trauma, pancreatitis, smoke inhalation, hematopoietic stem cell transplant, and transfusion-related acute lung injury.

ARDS is currently diagnosed based on the Berlin Definition of ARDS published in 2012 based on expert consensus [4]. It is clinically manifested by dyspnea and poor arterial oxygenation which is determined by the ratio of arterial partial pressure of oxygen to fraction of inspired oxygen ( $\text{PaO}_2/\text{FIO}_2$ ), along with bilateral opacities on chest imaging. ARDS is divided into 3 groups based on the degree of hypoxemia: mild ( $\text{PaO}_2/\text{FIO}_2$  201-300 mm Hg), moderate ( $\text{PaO}_2/\text{FIO}_2$ : 101-200 mm Hg), and severe ( $\text{PaO}_2/\text{FIO}_2 \leq 100$  mm Hg) and ventilator settings with a positive end-expiratory pressure (PEEP) or continuous positive airway pressure (CPAP)  $\geq 5$  cm  $\text{H}_2\text{O}$ . The mortality rate has been reported to be up to 50%, with increasing severity of ARDS leading to higher likelihood of mortality [5]. To date, no pharmacologic therapies have shown any benefit in reducing the high mortality of ARDS, and the primary treatment relies on treating underlying causes and supportive measures such as mechanical ventilation and fluid management [1]. Thus, effective therapies are needed.

### 1.2 Coronavirus Disease 2019 (COVID-19)

Coronavirus disease 2019 (COVID-19) is caused by severe acute respiratory syndrome coronavirus 2 (SARS-CoV-2), and was first reported in Wuhan, China in December 2019 [6]. In January 2020, the World Health Organization (WHO) declared the outbreak a global emergency after rapid spread to multiple other countries including the United States, Italy, Japan, Iran and others. The number of cases continues to increase exponentially with the number of cases surpassing 1,500,000 globally by April 10, 2020 [7].

SARS-CoV2 belongs to the Coronavirus (CoV) family which also includes the severe acute respiratory syndrome coronavirus (SARS-CoV) and Middle East respiratory

syndrome coronavirus (MERS-CoV) which led to epidemics 2003 and 2012, respectively. While COVID-19 shares a similar clinical presentation with SARS-CoV, it appears to have a higher transmission rate although the estimated basic reproductive number ( $R_0$ ) has been very dynamic as the number of cases continues to rise with increased testing availability [8-11]. The most common clinical symptoms of COVID-19 at onset are fever, cough, dyspnea, myalgia, and/or fatigue [10, 12, 13]. Less common symptoms included anosmia, headache, diarrhea, nausea, and vomiting. However, the clinical spectrum ranges widely from asymptomatic or mild illness to critical illness in a subset of patients with progression to ARDS, shock, and/or multi-organ failure leading to a case fatality rate variously estimated as 1%-4%. [14].

### **1.3 ARDS due to COVID-19 Disease**

Angiotensin converting enzyme-2 receptor (ACE-2) has been identified as a primary host receptor for cell entry utilized by SARS-CoV-2 similar to SARS-CoV [15, 16]. ACE-2 is highly expressed in multiple organs including but not limited to the oral cavity, human airway epithelia, myocardial cells, and kidney proximal tubule cells, and high expression may increase susceptibility to viral damage. It has been reported that approximately 50% of patients with COVID-19 pneumonia will progress to ARDS [12, 13, 17], with mortality approaching 50% in various studies [10, 12, 13, 17, 18]. Risk factors for ARDS and increased mortality include age (older than 60 years), presence of comorbidities such as hypertension, diabetes, heart disease, COPD, immunocompromised states, elevated markers of inflammation and higher disease severity as evidenced by high APACHE II, SOFA, and CURB-65 scores [10, 18-21]. At present, no effective antiviral treatment or vaccine is available; however, multiple clinical trials are evaluating the safety and efficacy of pharmacologic agents.

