### **2.3.2 Secondary endpoints:**

1. Clinical status at day 28 as determined by 6-point ordinal scale
2. Severity of ARDS at day 14
3. Oxygenation free days at day 28
4. Progression to mechanical ventilation or ECMO
5. Duration of mechanical ventilation and/or ECMO (ventilation/ECMO free days at day 28)
6. Duration of ICU stay (ICU free days at day 28)
7. Duration of hospital stay (time to discharge)
8. Overall survival
9. All-cause mortality at day 28

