### **2.3.3 Exploratory endpoints**

1. Changes in inflammatory markers (CRP, IL-6, IL-10, TNF- $\alpha$ )
2. Negative SARS-CoV-2 RT-PCR by day 28 (if available)
3. Changes in blood safety laboratories (CBC with differential, electrolytes, renal indices, liver function studies, LDH, coagulation studies if available)
4. Corticosteroid use and duration
5. Changes in chest imaging
6. Evolution of other end-organ damage (hepatic, renal, cardiovascular)
7. Changes in disease severity score (SOFA, CURB-65)
8. Duration of vasopressor use

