### 7.1 Baseline Pre-treatment Evaluation

- 7.1.1 History and physical (including vitals and oxygenation requirements)
- 7.1.2 SARS-CoV-2 RT-PCR testing
- 7.1.3 ARDS assessment
- 7.1.4 Complete Blood Count and differential (CBC)
- 7.1.5 Complete Metabolic Panel (CMP)
- 7.1.6 Coagulation studies: PT/aPTT, d-dimer, fibrinogen
- 7.1.7 Lactate Dehydrogenase (LDH)
- 7.1.8 C-Reactive Protein (CRP)
- 7.1.9 CXR and/or CT chest imaging
- 7.1.10 Urine or serum pregnancy test for females of childbearing potential
- 7.1.11 APACHE II score
- 7.1.12 Medical record review for concomitant medications
- 7.1.13 Clinical status assessed by the six-category ordinal scale (1 = discharged; 6 = death)

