Proportion of patients who have an improvement of at least two categories on a six category ordinal scale at day 14 and day 28 will be summarized using rate and their 95% confidence interval by treatment arms and compared with Chi-square tests. Proportion of patients with improvement will also be reported by cancer status. As exploratory analyses, improvement in clinical status will also be assessed using logistic regression, adjusting for potential confounders such as age, race/ethnicity, underlying condition, and severity of ARDS. Changes in the six-point ordinal scale, oxygen saturation, required FiO2, severity scores from baseline will be presented graphically and compared with paired t-tests or Wilcoxon signed rank tests, whichever are appropriate (comparisons are considered exploratory). Duration of overall survival will be days from date of randomization to date of death or date of last follow-up for censoring. Overall survival will be calculated using Kaplan-Meier survival curves with estimates of medians and 95% confidence intervals by each treatment arm and compared with a log-rank test (comparison is considered exploratory).

Laboratory data, which include inflammatory markers and chest imaging will be reported with appropriate summary statistics. Changes from baseline to post-treatment will be plotted for each patient over time and assessed using paired test methodologies when appropriate. Comparison between the two treatment groups will be exploratory with appropriate two-sample tests.

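### Baseline APACHE II, named as a mortality risk factor, enters no analysis, and the exploratory survival comparison ignores both this score and the randomization stratum: a minor efficiency point

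*Combined protocol and SAP*

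**What the plan says.** Section 1.3 names three severity scores as prognostic: "higher disease severity as evidenced by high APACHE II, SOFA, and CURB-65 scores". Section 7.1 lists "7.1.11 APACHE II score" as a baseline item for both arms, and the study calendar (6.1) marks it at baseline only.

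The severity-score endpoint in 2.3.3 is "Changes in disease severity score (SOFA, CURB-65". APACHE II is not in it and could not be, because there is no later value from which to form a change.

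"Overall survival" is the eighth of nine secondary endpoints in 2.3.2. In 8.5 the arms are shown by Kaplan-Meier curves and "compared with a log-rank test (comparison is considered exploratory". No covariate or stratum is mentioned, although 5.2 and 8.3 stratify randomization by moderate or severe ARDS.

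The one adjusted analysis in 8.5 is an exploratory logistic regression for clinical improvement, "adjusting for potential confounders such as age, race/ethnicity, underlying condition, and severity of ARDS". That list is illustrative rather than closed, but it does not name APACHE II, and the model is not for survival.

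**The concern.** The plan calls a score prognostic for death, asks sites to record it on every patient, and then gives it no role in the analysis of death. In a proportional-hazards setting, leaving out a strong predictor makes the marginal hazard ratio lie closer to 1 than the conditional one, and the unadjusted test loses power.

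With 30 patients per arm and few deaths, efficiency is worth having when it comes from data already collected. The trial is also open-label and single-center, so an adjustment chosen after the data are seen would carry little weight. If severity is to be taken into account in reading the survival curves, the model should be fixed in advance.

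**Working it through.** **Inputs from the documents.** 60 randomized patients, 30 per arm (8.2). Efficacy analyses use eligible randomized subjects (8.5). Mortality approaches 50% (1.3). Follow-up runs to day 28 (7.3).

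**The plan's own power figure.** The plan gives no power, hazard ratio or death count for survival. Its only power figure is 84% for the day-14 endpoint (10% v 35%, 30 v 36 patients, one-sided 7.5%). Using the pooled chi-square:
- pooled rate = (30×0.10 + 36×0.35)/66 = 0.236
- null SE = √(0.236×0.764×(1/30 + 1/36)) = 0.105
- alternative SE = √(0.09/30 + 0.2275/36) = 0.0965
- power = Φ((0.25 − 1.44×0.105)/0.0965) = 84.7%

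The figure reproduces. Nothing below bears on it.

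**Expected deaths, control mortality 50%.** Control arm: 30×0.5 = 15. MSC arm: 30×(1 − 0.5^HR), ignoring the score.
- HR 1: 15, total 30
- HR 0.5: 30×0.293 = 8.8, total about 24
- HR 0.4: 30×0.242 = 7.3, total about 22

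With a strong score the total at HR 0.5 rises to about 25. If control mortality were 35% (assumed), HR 0.5 gives about 16 to 17.

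**Unadjusted log-rank power (Schoenfeld).** Power = Φ(|ln HR|×√(d/4) − 1.96). At HR 0.5 and d = 24: Φ(0.693×2.449 − 1.96) = Φ(−0.26) = 39.7%. Survival power is low whichever analysis is used.

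**Effect of adjusting for one score.** The simulations used 30 v 30, exponential survival, censoring at day 28, control mortality 50%, a normal baseline score and no dropout. They compared the log-rank test with a Cox model containing treatment and the score. Treatment HR and score strength are assumptions.

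| Treatment HR | Score log-HR per SD | Log-rank | Adjusted Cox | Change (points) |
|---|---|---|---|---|
| 0.4 | 0 | 56.0% | 52.9% | −3.1 |
| 0.4 | 0.2 | 55.7% | 53.9% | −1.8 |
| 0.4 | 0.3 | 56.2% | 54.5% | −1.7 |
| 0.4 | 0.5 | 53% | 55% | +2 |
| 0.4 | 0.7 | 49% | 55% | +6 |
| 0.4 | 1.0 | 43% | 55% | +12 |
| 0.5 | 0 | 38.8% | 36.3% | −2.5 |
| 0.5 | 0.41 | 36.2% | 36.7% | +0.5 |
| 0.5 | 0.69 | 31.6% | 36.4% | +4.8 |
| 0.5 | 0.92 | 28.7% | 37.8% | +9.1 |

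The HR 0.4 rows use one-sided 2.5% (4,000 trials per scenario for the first three, 12,000 for the others). The HR 0.5 rows use two-sided 5% (6,000 trials). Repeat runs differ by a point or two. They give between −2 and 0 at 0.3, +1 to +3 at 0.5, +5 to +7 at 0.7 and +10 to +14 at 1.0. At one-sided 7.5% with HR 0.5 the pattern is the same: 59.3% to 58.6% with no association, and 49.0% to 59.9% at a score HR of 2.5 per SD.

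**Error rate.** With no treatment effect, both methods reject in 2.5 to 2.7% of the 12,000-trial runs at a nominal 2.5%.

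**Lower mortality.** With control mortality of 35% and HR 0.5 at two-sided 5%, the change runs from 27.5% to 24.0% with no association up to 21.4% to 25.1% at a score HR of 2.5 per SD. Fewer deaths mean a smaller gain.

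**Chance imbalance.** The difference in mean score between arms has SD √(2/30) = 0.26 score-SDs, so the 95% range is ±0.51. At a log-HR of 0.7 per SD this corresponds to a factor of exp(±0.7×0.51), about 0.70 to 1.42, on the hazard ratio. This ignores whatever the ARDS-severity stratification already balances.

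**The case against.** The strongest reply is that the comparison is exploratory by the plan's own label, has no stated alpha or power, and supports no claim. That stands. It limits the priority of the point, not its correctness.

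A reader might infer that the unadjusted log-rank test is invalid, or that a chance imbalance in APACHE II could not be told apart from an MSC effect. Neither is supported. The randomized test already allows for chance imbalance, as the error rates show, and stratification controls part of the severity difference. Nor is a marginal hazard ratio a biased conditional one; they are different quantities, and 8.5 does not list a hazard ratio among its outputs.

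A reader might also infer a certain loss of power. Section 1.3 gives no effect size. If the score predicts weakly or not at all, adjusting costs a little.

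Finally, 1.3 names age, comorbidities, inflammatory markers, SOFA and CURB-65 alongside APACHE II and does not rank them, and recording a score only to describe the arms is ordinary practice. This also stands: choosing APACHE II is a judgment. What remains is that it is one summary of severity, available at baseline and otherwise unused, and that the randomization stratum is missing from the survival test.

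**Conclusion.** The point holds as a low-priority efficiency improvement to an exploratory analysis of a secondary endpoint. The survival test is sound as planned, and the primary result and its 84% power are unaffected.

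At 50% control mortality and a hazard ratio of 0.4 to 0.5, adjustment is worth about 5 to 14 points of power if APACHE II is a strong predictor (log-HR 0.7 to 1.0 per SD), is close to neutral at 0.3 to 0.5, and costs about 3 points if it has no prognostic value. Lower mortality shrinks the gain. Even adjusted, power at two-sided 5% and HR 0.5 stays near 36 to 38%.

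These figures rest on proportional hazards, a normally distributed score, no dropout, and a prognostic strength that the documents do not supply. The simulations did not include the ARDS-severity stratum, so they do not measure what stratifying adds or costs.

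**What to change.** In 8.5, prespecify a Cox model for overall survival from randomization to day 28 in the randomized patients, with treatment and baseline APACHE II as one continuous covariate, stratified by ARDS severity (moderate or severe) as used at randomization. Replace any missing baseline score by the overall mean, so that no randomized patient is dropped. Report the adjusted hazard ratio with its 95% interval beside the Kaplan-Meier curves and the log-rank test, and keep the comparison labelled exploratory. Add no further covariates: about 22 to 25 deaths are expected if MSCs work at the hazard ratios above, and about 30 if they do not.

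The cost is a few lines of SAP text and one model on data already collected, with no new visits or patients. The hazard ratio becomes conditional on the score and stratum, which should be stated when it is reported, and a little power is lost if APACHE II proves not to be prognostic.

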### **1.4 COVID-19-associated coagulopathy (CAC)**

Abnormalities in coagulation parameters have been observed in patients hospitalized with COVID-19 disease [12, 19, 22, 23]. Most common are elevations in fibrinogen and D-dimer, which may correlate with a rise in inflammatory markers. However, some patients with severe COVID-19 disease develop classic disseminated intravascular coagulopathy (DIC) with moderate to severe thrombocytopenia, prolongation of PT/aPTT, elevated D-dimer, and fibrinogen less than 100 mg/dL. Tang et al reported that use of low molecular weight (LMWH) or unfractionated (UFH) heparin was associated with decreased mortality in patients with severe COVID-19 disease [24]. Conversely, progressively increasing D-dimer levels were associated with increased mortality. Based on these (and related) findings, monitoring of platelet counts, PT/aPTT, D-dimer and fibrinogen levels is strongly recommended. While the use of therapeutic anticoagulation in patients with severe COVID-19 disease is still under study, prophylactic low dose heparin anticoagulation is recommended in the absence of active bleeding or other contraindications.

## 1.5 Mesenchymal Stromal Cells (MSCs) for Inflammatory Disorders, including ARDS

Mesenchymal stromal cells have shown benefit in patients with inflammatory and immune-related disorders, such as inflammatory bowel disease [25], rheumatoid arthritis [26], type 1 diabetes mellitus [27-29], systemic lupus erythematosus [30-33], multiple sclerosis [34], and acute graft versus host disease (aGVHD) [35] as well as lung disease [36-38]. MSCs are a cellular component of the supportive microenvironment that function as multipotent progenitor cells with the capacity to differentiate into mesodermal lineages, such as adipocytes, osteocytes, and chondrocytes [39, 40]. MSCs also contribute to tissue repair [41-43]. They also have anti-inflammatory properties and increase the activity of T regulatory cells, which may benefit development of immune tolerance [44-47]. Since MSCs do not express class II human histocompatibility antigens (HLA) or co-stimulatory molecules (CD40, CD40L, CD80, and CD86) required for T cell activation, even allogeneic (banked) MSC appear to induce little alloreactivity after administration [48, 49]. MSCs also secrete antimicrobial peptides that enhance bacterial clearance and improve survival [50-52]. These inherent qualities of MSCs make them a promising candidate for the treatment of lung injury without toxicities.

Multiple preclinical studies have shown that MSCs can be used for treating lung injury [53-55]. Chan et al showed that human MSCs administered to aged mice infected with H5N1 prevented or reduced lung injury, thereby increasing oxygenation. The MSCs reduced pro-inflammatory cytokines and increased survival [56]. MSC administration similarly reduced proinflammatory cytokines and chemokines, and pulmonary inflammation in mice with H9N2 avian influenza induced lung injury [57]. MSCs also attenuate lung injury in mice and *ex vivo* human lungs after injury by live bacterial infections [51, 58]. In addition, MSCs may secrete paracrine factors that improve the rate of alveolar fluid clearance [59, 60]. Based on these preclinical findings, MSCs were deemed to be a promising form of adoptive cell therapy for the treatment of ARDS.

Several phase 1 and 2 studies evaluating the safety of MSCs as treatment for a variety of lung diseases (idiopathic pulmonary fibrosis, COPD and ARDS) have confirmed tolerability of this approach [36-38, 61, 62]. A case report of two patients with severe, refractory ARDS treated with MSC from allogeneic bone marrow (2 million cells/kg i.v.) had significant improvement of respiratory and end-organ failure, as well as reduction in inflammatory cytokines [63]. In a phase 1, dose-escalation study using bone marrow derived allogeneic MSCs for moderate to severe ARDS, no infusion or treatment related adverse events were reported in 9 recipients [62]. Two patients died, but this was considered unrelated to infusion of the MSCs. Given the mortality associated with COVID-19 induced ARDS, Leng et al. conducted a pilot study of MSC administration in patients with confirmed SARS-CoV-2 pneumonia. They reported improvement in pulmonary function and symptoms, and a decrease in pro-inflammatory cytokines such as TNF- $\alpha$  and an increase in anti-inflammatory IL-10 [21]. They were also able to show improvement, although not statistically significant, in the disease severity scores such as SOFA.

